15.9 Expanded Pharmacokinetic Sampling Procedures – Applicable to Select Sites Only

For those subjects who have consented to participate in the expanded tozadenant PK sampling, [Sections 15.9.1](#) and [15.9.2](#) should be referred to instead of [Sections 6.2.3.4](#) (Baseline Assignment and Dispensing and Investigational Medicinal Product) and [6.2.4](#) (Visit 3/Week 2), respectively.

Pharmacokinetic blood samples for determination of plasma tozadenant concentration will be collected at the Week 2 study visit at select sites only. The Schedule of Events for subjects participating in Expanded PK Sampling is provided in [Table 4](#).

15.9.1 Baseline (Visit 2) Assignment and Dispensing and Investigational Medicinal Product for Subjects Participating in Expanded PK Sampling (Replacement Section for [Section 6.2.3.4](#))

1. For patients meeting all entry criteria, complete the IMP assignment transaction using the IXRS by following the procedures provided.
 - a. Dispense the open-label IMP bottle(s) assigned by the IXRS to the patient for this study visit. Each bottle consists of either 50 tablets of 120 mg tozadenant or 100 tablets of 60 mg tozadenant.
 - b. Record the date IMP was dispensed in IMP dispensing records including patient number, assigned IMP bottle number(s), and date and time IMP was dispensed.
 - c. Review the dosing instructions for the IMP with the patient, answer any questions, and remind the patient to return the IMP (including all used, unused and partially used bottles) at the next visit.
 - d. Patients will be instructed to take either two (2) 60 mg tablets or one (1) 120 mg tablet of the dispensed IMP by mouth twice daily (BID), in the morning and in the evening preferably at the same time each day, for a total of either two (2) 120 mg tablets or four (4) 60 mg tablets per day. The evening dose should be approximately 12 hours after the morning dose. Patients will be instructed to take their morning and evening doses 1 hour before or 2 hours after a meal and to refrain from eating for 1 hour after dosing. Patients should take the first dose of IMP at home after the Baseline Visit.
2. Instruct the patient to take the first dose of IMP at home on the evening of dispensation.
3. Ensure that the patient understood the dosing instructions and the use of the extra doses included in the bottle if visit delayed and/or use of visit window.
4. **Subjects participating in the expanded tozadenant PK sampling will be advised to refrain from taking their 120 mg IMP dose on the day of the Week 2 visit, prior to the visit.**
5. Schedule the Week 2 visit. If needed, use the visit window in relation to the date of the Baseline visit.

**15.9.2 Visit 3 (Week 2) for Subjects Participating in Expanded PK Sampling
(Replacement Section for Section 6.2.5)**

Note: Confirm the arrangement for laboratory sample pick-up on the day of the Week 2 visit with the courier (see Central Laboratory Procedures Manual).

1. For all applicable patients: Verify continuation of (or any change to) contraceptive method since Screening and document.
2. **Obtain sample for the following laboratory tests and record the date and time of collection:**
 - a. **Expanded PK blood sample(s) for plasma tozadenant concentration.**
 - i. **Collect one (1) pre-dose/trough PK blood sample before the administration of IMP. Record the date and time of PK sample collection. Document the date and time of the previous IMP dosing.**
 - ii. **Administer the 120mg dose during the visit from the IMP bottle previously dispensed at Baseline visit. Record the date and time when the patient took the 120mg dose of IMP.**
 - iii. 

Note: For processing, labeling and shipping of samples, follow the instructions provided in the Central Laboratory Procedures Manual.

- b. Hematology and chemistry (inclusive of liver function tests).
- c. TSH, free T3, and free T4.
- d. For females of childbearing potential: urine pregnancy test.
- e. Urinalysis.

Note: For processing, labeling and shipping of samples, follow the instructions provided in the Central Laboratory Procedures Manual.

3. Assess AEs by asking open-ended queries and record the assessments.
4. Record concomitant medication use; assess and record any changes to anti-PD medication dose or regimen.
5. Obtain and record BP and pulse measurements after at least 5 minutes supine rest and again after standing for approximately 1 and 3 minutes.
6. Obtain 12-lead ECG. Ensure the ECG is collected when the patient is not experiencing dyskinesia that would interfere with an adequate recording. Assess any changes from Baseline for clinical significance.
7. Record the date and approximate time of the most recent dose of levodopa taken prior to the UPDRS assessment.

8. Perform the following assessments in the ON state:
 - a. Perform full UPDRS Parts I, II, III (motor) and IV. UPDRS Part III should be performed approximately 1 to 3 hours after the patient has taken a scheduled dose of levodopa (preferably their morning dose of levodopa). UPDRS in the ON state will be measured at a time representative of the ON state in that patient, not in “best” ON.
 - b. Administer the following assessments:
 - CGI-I.
 - PGI-I.
 - c. Have the patient complete the following self-assessment questionnaire:
 - ESS.
9. Administer the following assessments (may be done anytime during visit):
 - a. C-SSRS.
 - b. mMIDI. (Note: After Baseline, if patient has one or more positive modules on the mMIDI, their continued participation in the study should be discussed with the Medical Monitor.)
 - c. Assessment for episodes of sudden onset of sleep.
 - d. Healthcare Resource Utilization.
10. Collect the IMP (including all used, unused and partially used bottles) dispensed at the Baseline Visit.
 - a. Record the date and approximate time when the patient took the last dose of IMP.
 - b. Assess and document IMP accountability and compliance (document any missed dose(s), lost tablets and number of tablets taken).
 - c. Review and reconcile any discrepancies with the patient.
11. Dispense the open-label IMP bottle(s) assigned by the IXRS to the patient for this study visit. Each bottle consists of either 100 × 60 mg tablets or 50 × 120 mg tablets.
 - a. Record the date IMP was dispensed in IMP dispensing records.
12. Review the dosing instructions for the IMP with the patient, answer any questions, and remind the patient to return the IMP (including all used, unused and partially used bottles) at the next visit.
13. Ensure that the patient understood the dosing instructions and the use of extra doses included in the bottle if visit delayed and/or use of visit window.
14. Schedule the next study visit (Week 4). If needed, use the visit window in relation to the date of the Baseline visit.

Table 4: Schedule of Events/Evaluations for Subjects Participating in Expanded PK Sampling

Study Period	Screening ^a	Baseline Predose	Open-Label Treatment (52 weeks)						Safety Follow-Up	Early Termination ^x	Unschedule d	
	Study Week ^b -6 to -1	BL	2 (± 3 d)	6 (± 3 d)	12 (± 3 d)	24 (± 7 d)	36 (± 7 d)	52 (± 14 d) [16 weeks]	56 (28 ± 3 d after last dose of IMP)			
Assessments	Study Visit	V1	V2	V3	V4	V5	V6	V7	V8	V9	B98	B97
Written Informed Consent	X											
Demographics and Medical History, including neurological and PD history	X											
Recording of concomitant and anti-PD medications	X	X	X	X	X	X	X	X	X	X	X	X
BP ^c , pulse ^c	X ^d	X ^d	X	X	X	X	X	X	X	X	X	X ^e
12-lead ECG ^f	X	X ^g	X	X	X	X	X	X	X	X	X	X ^e
Weight (include height at Screening)	X				X	X		X	X	X	X	X ^e
Physical and neurological examination	X				X	X	X	X	X	X	X	X ^e
PD diary training and diary concordance session	X											
Modified Hoehn and Yahr staging (observed ON; OFF estimated per history) ^h	X											
UPDRS Parts I, II, III and IV ⁱ	X	X	X	X	X	X	X	X	X		X	
MMSE-II (in ON state)	X											
mMIDI ^j	X		X	X	X	X	X	X	X	X	X	X ^e
ESS ^h		X	X	X	X	X	X	X	X	X	X	
PD diary collection (phone call prior to start of 3 consecutive 24 hour diary completion periods)	X ^k	X ^k			X ^l	X ^l			X ^l		X ^m	
PD diary review	X	X			X	X			X ^m		X ^m	
C-SSRS	X	X	X	X	X	X	X	X	X	X	X	X ^e
CGI-I ^h			X	X	X	X	X	X	X		X	
PGI-I ^h			X	X	X	X	X	X	X		X	
PDQ-39 ^h		X				X			X		X	
Sudden onset of sleep	X	X	X	X	X	X	X	X	X	X	X	
Fall questionnaire		X					X		X		X	
Healthcare Resource Utilization			X	X	X	X	X	X	X		X	
Non-motor Symptom Questionnaire ^h		X					X		X		X	
EQ-5D-5L ^h		X					X		X		X	
Recording of AEs	X ⁿ	X ⁿ	X	X	X	X	X	X	X	X	X	X

Assessments	Study Period	Baseline	Open-Label Treatment						Safety	Early	Unschedule
	Study Week ^b	Predose	(52 weeks)						Follow-Up	Termination ^x	d
	Study Visit		2	6	12	24	36	52	56		
	-6 to -1	BL	(± 3 d)	(± 3 d)	(± 3 d)	(± 7 d)	(± 7 d)	(± 14 d) [16 weeks]	(28 ± 3 d after last dose of IMP)		
	V1	V2	V3	V4	V5	V6	V7	V8	V9	B98	B97
Laboratory tests: hematology ^o , chemistry ^p (including thyroid function ^q)	X	X	X	X	X	X	X	X	X	X	X ^e
FSH test, females who are postmenopausal for < 2 years	X										
Method of contraception ^r	X	X	X	X	X	X	X	X	X	X	X ^e
Urine pregnancy test, females of childbearing potential ^s	X	X	X	X	X	X	X	X	X	X	X ^e
Urinalysis ^t	X	X	X	X	X	X	X	X	X	X	X ^e
Review of inclusion/exclusion criteria	X										
Final verification of eligibility		X									
Tozadenant blood sampling											
IMP dispensing and/or return^v		X ^w	X	X	X	X	X	X		X	X ^e
eCRF completion	X	X	X	X	X	X	X	X	X	X	X

AE, adverse event; BP, blood pressure; CGI-I, Clinical Global Impression of Improvement; C-SSRS, Columbia-Suicide Severity Rating Scale; d, day; ECG, electrocardiogram; eCRF, electronic case report form; ESS, Epworth Sleepiness Scale; ET, Early Termination; FSH, follicle stimulating hormone; IMP, investigational medicinal product; mMIDI, Modified Minnesota Impulse Disorders Interview; MMSE-II, Mini-Mental State Exam – Second Edition (MMSE-II); PD, Parkinson’s disease; PDQ-39, Parkinson’s Disease Quality of Life Questionnaire; PGI-I, Patient’s Global Impression of Improvement; UPDRS, Unified Parkinson’s Disease Rating Scale; V, Visit.

Footnotes

^a Screening period may not exceed 6 weeks.

^b Visit windows for scheduled visits after Baseline (V2) are in relation to the date of the Baseline Visit (V2).

^c Obtain and record BP and pulse measurements after at least 5 minutes supine rest and again after standing for approximately 1 minute and 3 minutes.

^d At Screening and Baseline (before dosing), obtain and record serial BP and pulse measurements after at least 5 minutes supine rest and again after standing for approximately 1 and 3 minutes. Repeat these BP and pulse measurements 2 more times approximately 10 minutes apart.

^e Optional activities (e.g., additional assessments for evaluation of AEs) that may be performed at the investigator’s discretion.

^f A resting supine 12-lead ECG will be collected after the patient has been in a supine position for a minimum of 5 minutes. Ensure the ECG is collected when the patient is not experiencing dyskinesia that would interfere with an adequate recording.

^g At Baseline, obtain three 12-lead ECGs (i.e., 3 serial readings, performed several minutes apart). Ensure the ECGs are collected when the patient is not experiencing dyskinesia that would interfere with an adequate recording.

^h To be collected during patient’s ON state.

ⁱ UPDRS to be measured in ON state. UPDRS Part III should be measured approximately 1 to 3 hours after patients have taken a scheduled dose of levodopa (preferably their morning dose of levodopa). Patients will be instructed to have already taken their normally scheduled dose of levodopa and their IMP before arriving at the study site in order to have their UPDRS Part III evaluated in the ON state. UPDRS in the ON state will be measured at a time representative of the ON state in that patient, not in the patient’s “best” ON.

Table 4: Schedule of Events/Evaluations for Subjects Participating in Expanded PK Sampling (continued)

^j At Screening, send patient for structured clinical interview if one or more positive mMIDI modules. If the structured clinical interview confirms that the subject does not have an ICD, he/she will not be considered ineligible on that basis. After Baseline, if patient has one or more positive modules on the mMIDI, their continued participation in the study should be discussed with the Medical Monitor.
 
^k The 3-day practice diary during the Screening Period and the 3-day Baseline diary must both be valid in order to enroll a patient. The trainer/rater will call the patient before the scheduled start of the diary completion periods to remind him or her to keep the PD diary and to review completion instructions. The patient will also be reminded to send the completed practice diary to the trainer/rater and to bring their Baseline diary to the Baseline Visit. If the practice or Baseline diary is invalid, the patient may be retrained and complete another practice or Baseline diary within the 6-week window of the Screening Period, if the patient is otherwise eligible for the study.
 
^l PD diary collected over the 3 consecutive 24-hour periods before the day of the scheduled study visits on Weeks 12, 24 and 52. The PD diary trainer/rater will call the patient before the scheduled start of the 3-day PD diary completion period (at the latest, on the last working day before the scheduled start of the PD diary completion) and review completion instructions. The patient will also be reminded to bring their PD diary to the visit. The trainer/rater will instruct the patient if the PD diary contains missing and/or invalid entries to reinforce instructions for appropriate completion.
 
^m Done only if the ET date coincides with the scheduled diary collection return date.
 
ⁿ Pretreatment AEs.
 
^o Hematology tests: Hemoglobin concentration, hematocrit, red blood cell count, total and differential white blood cell, thrombocyte (platelet) count.
 
^p Blood chemistry (including liver function) tests: Aspartate amino transferase (AST), alanine amino transferase, (ALT), gamma-glutamyl transpeptidase (GGT), alkaline phosphatase (ALP), lactate dehydrogenase (LDH), total bilirubin (conjugated and unconjugated), albumin, creatinine, urea/BUN, bicarbonate, uric acid, total protein, sodium, chloride, potassium, calcium, phosphate, glucose, cholesterol, creatine phosphokinase (CK).
 
^q TSH, free T₃, and free T₄.
 
^r For applicable patients: At Screening, document method of contraception used by patient. At subsequent visits, verify continuation of (or any change to) contraceptive method.
 
^s For females of childbearing potential: urine pregnancy test.
 
^t Urinalysis: Specific gravity, pH, ketones, blood, protein, glucose. If urine dipstick is positive for leukocytes, protein, or erythrocytes, a microscopic evaluation and culture will be performed.
 
[REDACTED]
 
^v Patients will be instructed to take the assigned dose of open-label tozadenant by mouth BID, in the morning and in the evening preferably at the same time each day. The evening dose should be approximately 12 hours after the morning dose. Patients will be instructed to take their morning and evening doses at least 1 hour before or 2 hours after a meal and to refrain from eating for at least 1 hour after dosing.
 
^w Patients will be instructed to refrain from taking their 120 mg IMP dose on the day of the Week 2 visit, prior to the visit.
 
^x If patient has discontinued IMP, perform Early Termination Visit as soon as possible after the last dose of IMP. If patient took the last dose of IMP 28 or more days prior to the Early Termination Visit, a Safety Follow-Up Visit (Section 6.2.19) is not required.


Table 4.1: Schedule of Events/ Evaluations for Hematology Monitoring

Assessments	Study Period	Open-Label Treatment (52 weeks)					Weekly monitoring ^b (if required)	
	Study Week	4 (±3 d)	8 (±3 d)	10 (±3 d)	16 (±3 d)	20 (±3 d)	44 (±14 d)	
	Study Visit	V3.5	V4.3	V4.8	V5.3	V5.8	V7.5	
Laboratory test: hematology ^a		X	X	X	X	X	X	X
Recording of AEs								X
Recording of concomitant and Anti-PD medications								X
eCRF completion		X	X	X	X	X	X	X

^aHematology tests: Hemoglobin concentration, hematocrit, red blood cell count, neutrophils, total and differential white blood cell, thrombocyte (platelet) count.

^bOnly for patients that require weekly hematology monitoring per [section 4.3.2](#). To be captured as an unscheduled visit in EDC/RAVE.

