
Criteria for Patient Discontinuation from Study
	
Patients are free to withdraw from the study at any time, without prejudice to their continued care.
 
Patients may be discontinued from the study at any time if clinically significant out-of-range laboratory values, clinically significant abnormal findings on physical examination, or intolerable TEAEs put the patient at additional risk, as judged by the investigator. Patients experiencing TEAEs considered to be study drug-related and not tolerated by the patient will be discontinued from the study. Patients must be discontinued from the study if the absolute neutrophil count is less than 1000/mm³ (or 1.0 x 10E9/L). A complete list of reasons for patient discontinuation is located in Section 4.3 of the protocol.
 
The Study Sponsor (Biotie Therapies, Inc.) has the right to terminate the study at any time.
 
All patients who discontinue prematurely from the study will be requested to return to the study site as soon as possible to complete the safety and efficacy evaluations outlined for an Early Termination Visit in the Schedule of Events/Evaluations (Table 1). The Early Termination Visit should be done while the patient is taking IMP, if possible. After Early Termination, the patient will also be asked to return for a Safety Follow-Up Visit to be scheduled 28 days after the last dose of IMP, unless the Early Termination Visit itself occurred 28 or more days after the last dose of IMP.
 
All TEAEs will be followed until resolution, return to Baseline level, or stabilization.

PROTOCOL SYNOPSIS

Sampling for Tozadenant Plasma Drug Concentrations
	
Pharmacokinetic (PK) blood samples for determination of plasma tozadenant concentration will be collected at the Week 2 study visit. [REDACTED] blood sample will be collected at the most convenient time during the visit (“Sparse PK Sampling”). [REDACTED] PK blood samples may be collected (“Expanded PK Sampling” - additional details are provided in Appendix 15.9). On the morning of the Week 2 visit, participating subjects will refrain from taking their 120 mg IMP dose until after collection of a predose/trough PK sample. [REDACTED]

Sample Size Justification
	
Approximately 645 patients will be screened, assuming a 30% screen failure rate, to enroll 450 patients.

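### Expanded-PK patients are told in one place to take the Week 2 morning tozadenant dose before the visit and in others to withhold it

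*Protocol*

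**What the plan says.** Appendix 15.9 covers only patients who consent to expanded sampling; those samples "will be collected at the Week 2 study visit at select sites only". Table 4 is their schedule of events.

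In Table 4 the UPDRS row carries footnote i and is marked at Week 2. The footnote says "Patients will be instructed to have already taken their normally scheduled dose of levodopa and their IMP before arriving at the study site", so that Part III is rated in the ON state. It gives no Week 2 exception, and Table 1 footnote i has the same sentence for the study as a whole. The synopsis (Overview of Study Procedures) gives the instruction for a list of visits that includes Week 2. Sections 6.1 and 7.2 repeat it without naming visits.

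On the other side:

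- Table 4 footnote w tells these patients to "refrain from taking their 120 mg IMP dose on the day of the Week 2 visit, prior to the visit".
- Section 15.9.1 item 4, applied at Baseline dispensing, covers the morning of the Week 2 visit: "Subjects participating in the expanded tozadenant PK sampling will be advised to refrain from taking their 120 mg IMP dose".
- The synopsis PK row says that "participating subjects will refrain from taking their 120 mg IMP dose until after collection of a predose/trough PK sample".
- Section 15.9.2 item 2.a has the predose sample drawn first, then the instruction "Administer the 120mg dose during the visit from the IMP bottle previously dispensed at Baseline visit".

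SAP 9.7.2.1 treats the predose sample as a trough and summarizes it, together with samples at 3, 5, 6 and 8 hours after dosing.

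**The concern.** The same dose cannot be both taken before arrival and withheld until after a blood draw. The instruction to take it appears in the table written for the patients who must withhold it, so the conflict is not only between general text and an appendix.

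What is at stake is the predose sample. If tozadenant has been taken that morning, the sample is a postdose sample carrying a trough label. Week 2 is the only planned PK visit, so no later visit supplies a replacement. The trough summary would include the wrong quantity, and the time-zero point of AUC0-last would be affected.

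**Working it through.** No calculation applies, and the plan gives no figure to reproduce. The check is a comparison of texts.

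**1. Does footnote i reach Week 2?** It does so through the row mark, not by name. The UPDRS row of Table 4 is marked at Week 2 and its label carries footnote i. The synopsis overview does name Week 2.

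**2. Where is each instruction given?**

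- Already taken: five places in the protocol, namely the synopsis overview, Table 1 footnote i, Section 6.1, Section 7.2 and Table 4 footnote i. Only the last is specific to expanded-PK patients.
- Withhold: three places, namely the synopsis PK row, Section 15.9.1 item 4 and Table 4 footnote w. All three are specific to expanded-PK patients. The sampling order in Section 15.9.2 item 2.a agrees with them.

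**3. Does the appendix displace the general text?** Only in part. The opening of 15.9 substitutes its two subsections for Sections 6.2.3.4 and 6.2.4. Sections 6.1 and 7.2 are not on that list, so their instruction still applies on its face. Footnote i is itself inside the appendix.

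**4. Where would a coordinator see the exception?** Footnote w is attached to the Baseline cell of the IMP dispensing row. In the visible text, the Week 2 UPDRS entry leads to footnote i and not to footnote w.

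**5. What follows if footnote i is obeyed?** Doses are about 12 hours apart (footnote v: "The evening dose should be approximately 12 hours after the morning dose"), so the planned trough falls about 12 hours after the previous evening's dose. A same-morning dose makes the draw a postdose one. If item 2.a.ii were then applied literally, a further 120 mg would be given in clinic. That drug would be on top of the morning dose in the postdose samples too, so the problem could extend beyond the predose sample of a five-sample profile (1 predose + 4 postdose).

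**6. Would it be noticed?** Section 15.9.2 item 2.a.i requires the date and time of the previous IMP dose to be documented with the predose sample. A same-morning dose would therefore be on record.

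**The case against.** The strongest reply is that footnote i is generic UPDRS text. Its row is also marked at Screening and Baseline, before any patient has tozadenant, so its IMP clause plainly cannot apply at every marked visit. The operative procedure is consistent: patients are told at Baseline to withhold, the Week 2 UPDRS step in Section 15.9.2 (item 8a) asks only for a prior levodopa dose, and item 2.a.i records the last IMP dose. Several sections send expanded-PK sites to Appendix 15.9, and the synopsis gives the exception in its PK row.

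Most of this stands. It shows that the intent is clear and that a careful site would probably withhold the dose. It does not make footnote i correct, and the synopsis overview does name Week 2.

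A reader might go further and infer a timing error of 9 to 11 hours, by taking the sample to fall 1 to 3 hours after tozadenant (12 − 3 = 9; 12 − 1 = 11). The documents do not support that. The rule that "UPDRS Part III should be measured approximately 1 to 3 hours after patients have taken a scheduled dose of levodopa" times the motor examination, not the PK draw, and nothing says that tozadenant is taken with that levodopa dose.

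A reader might also expect double dosing in clinic. That needs the Baseline instruction to be missed and the site to dose again after recording a same-morning dose. It is possible, but the plan as a whole does not direct it.

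**Conclusion.** The contradiction is real and minor. Table 4 footnote i and the synopsis overview, as written, tell expanded-PK patients to take a dose that footnote w, Section 15.9.1 item 4 and the synopsis PK row tell them to withhold. The specific text settles the intent, so this looks like a sentence carried over from Table 1 without its exception, not an undecided design question.

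The exposure is limited to sites or patients who follow the general instruction. How many that would be, and how mistimed their samples would be, cannot be derived from the documents. Section 15.9.2 item 2.a.iii and the PK footnote of Table 4 are redacted and may hold further sampling instructions, but they would not change what footnote i says.

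It would be wrong to infer that the safety conclusions are affected. Expanded PK is descriptive, is done at select sites, and is in neither the primary nor the secondary objective.

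**What to change.** Add to Table 4 footnote i: *except at Week 2, when IMP is withheld until after the predose PK sample (see footnote w)*. Add the same exception, pointing to Appendix 15.9, to the visit instruction in the synopsis overview and, for consistency, to Sections 6.1 and 7.2. The levodopa timing stays as it is.

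Optionally, add one line to SAP 9.7.2 saying that a sample drawn after a same-morning IMP dose is not summarized as a trough. The SAP 3.1.4 population definition already asks for adequate, analyzable samples, so this is a clarification. If the line is added, it should leave the profile out of the PK parameters and not set the predose value to missing. SAP 9.7.2.2.1 replaces a missing predose concentration with zero, which would not suit a patient dosed twice daily for about two weeks.

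The cost is one phrase in four places and, if wanted, one SAP line. It adds no patients, visits or samples.
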